**If your site utilizes the CIRB as your IRB of record**

*No recommended IRB level of review is provided by the Alliance since the CIRB is the IRB of record for this trial. The site has 30 days after the posting of this amendment to implement it at their site. Please refer to the amendment application and CIRB guidelines for further instructions.*

**If your site utilizes a local IRB as your IRB of record**

*Expedited review is allowed. IRB approval (or disapproval) is required within 90 days. Please follow your local IRB guidelines. The proposed changes in this amendment are minor and do not affect the overall risk/benefit ratio.*

### **UPDATES TO PROTOCOL:**

#### **Cover Page (Page 1)**

## Study Resources (Page 2)

## CTSU Address and Contact Information (Page 3)

The CTSU Contact Information table has been updated to reflect current CTSU boilerplate language.

## Section 4.0 (Patient Registration)

All text in this section has been updated to reflect current CTSU boilerplate language.

## Section 6.1 (Data Collection and Submission)

All text in this section has been updated to reflect current CTSU boilerplate language.

## Section 6.1.3 (IRB Terminations)

A new section has been added to note institutions must not close a trial with the IRB of record until a formal notice from the Alliance regarding termination to patient follow-up has been received.

## Section 6.3.3 (Using TRIAD Image Submission)

All text in this section has been updated to reflect current CTSU boilerplate language.

## Section 10.1 (Vemurafenib)

In the 1st sentence of the 1st paragraph in the *Procurement* section, the phrase “RxCrossroads by McKesson” has replaced “Biologics” to accurately reflect the drug distributor.

## Section 10.2 (Cobimetinib)

In the 1st sentence of the 1st paragraph in the *Procurement* section, the phrase “RxCrossroads by McKesson” has replaced “Biologics” to accurately reflect the drug distributor.

## UPDATES TO CONSENT FORM:

No changes have been made to the informed consent document.

**Replacement protocol and model consent documents have been issued.**

---

## PHASE II TRIAL OF BRAF/MEK INHIBITORS IN PAPILLARY CRANIOPHARYNGIOMAS

### Key Pre-Registration Eligibility Criteria (see [Section 3.2](#))

- Local diagnosis of papillary craniopharyngioma
- Tissue slides available for central path review

### Key Registration Eligibility Criteria (see [Section 3.3](#))

- Histologically proven papillary craniopharyngioma as documented by central path review
- Measureable disease, defined as  $\geq 1\text{cm}^3$  present on imaging
- Surgery completed  $\geq 21$  days from registration.
- Cohort A: No prior therapy other than surgery. Progressive disease allowed but not required.
- Cohort B: Prior radiation therapy and progressive disease required. Completion of RT  $\geq 14$  days from registration.
- No prior treatment with BRAF or MEK inhibitors
- Steroid dosing stable for  $\geq 4$  days
- Non pregnant and non nursing
- Age  $\geq 18$  years
- ECOG Performance Status  $\leq 2$
- No comorbid conditions as outlined in [Section 3.3.6](#).
- No CYP3A4 inducers and inhibitors and CYP1A2 substrates within 14 days of registration

[figure not shown]
### Required Initial Laboratory Values

(see [Section 3.3.8](#))

ANC	$\geq 1500/\text{mm}^3$
Platelets	$\geq 100,000/\text{mm}^3$
Creatinine	$\leq 1.5 \text{ mg/dL}$
OR	
Calc. Creatinine Clearance (see Alliance website)	$\geq 45 \text{ mL/min}$
Total Bilirubin	$\leq 1.5 \times \text{ULN}$
AST / ALT	$\leq 2.5 \times \text{ULN}$

### Schema

1 Cycle = 28 Days

\* Submit slides for Central Pathology BRAF IHC within 28 days after pre-registration. Once slides are received at BWH/DFCI, results will be returned within 14 days. Register patient within 21 days of result notification. See Sections [4.3](#), [4.4](#), and [6.2.1](#) for complete instructions.

\*\* Discontinue vemurafenib + cobimetinib at progression, unacceptable adverse event, or drug hold  $>28$  days. After discontinuation of vemurafenib and cobimetinib, subsequent treatment is at the discretion of the treating physician.

\*\*\* Patients on Cohort A may continue treatment with vemurafenib and cobimetinib beyond 5 cycles in special circumstances with study chair approval. See [Section 7.1.1](#) for more information.

Patients will be followed for 5 years from study registration (Step 1) or until death, whichever comes first.

**Please refer to the full protocol text for a complete description of the eligibility criteria and treatment plan.**

Study components allowed to be completed at non-registering institutions: Surgery for patients enrolled on Cohort A. Surgery and Radiation for patients enrolled Cohort B. Supporting documentation must be submitted per [Section 6.1.1](#) even if performed at non-registering institution.

## 1.0 BACKGROUND

### 1.1 The natural history of craniopharyngioma

Craniopharyngiomas, which occur at an average age-adjusted incidence rate of 0.18 per 100,000, are epithelial tumors that arise in the pituitary stalk along the path of the craniopharyngeal duct. There are two main subtypes of craniopharyngiomas, the adamantinomatous form that is more common in children and the papillary form that predominantly occurs in adults. Located in or above the sella turcica, these tumors grow adjacent to the optic chiasm and often extend to involve the hypothalamus, cranial nerves, the ventricular system, visual pathways and major blood vessels at the base of the brain. Craniopharyngiomas can cause profound clinical sequelae both in the pediatric and adult populations, both through mass effect at presentation and through morbidity of treatment. At initial presentation, a broad range of signs and symptoms can be observed. Visual deficits, neuroendocrine deficiencies and severe headaches are common. Attempted surgical resection is usually the initial treatment of craniopharyngioma, but because these tumors adhere to critical brain and vascular structures, incomplete resection is common. Incompletely excised tumors have a propensity to recur, frequently with cysts, with firm adhesions between the recurrent tumor and the surrounding structures such that curative surgery is exceedingly difficult. Either the cystic, solid or both components, of craniopharyngiomas can cause significant symptomatic mass effect. As a result, most patients suffer lifelong sequelae that include panhypopituitarism, visual defects, impaired intellectual function and wide-ranging hypothalamic dysfunction leading to sleep disorders, abnormal thermo-regulation, and diabetes insipidus as well as hyperphagia and uncontrollable obesity. Radiation therapy, often used as an adjunct after surgery, can contribute to these complications. The debilitating long-term morbidities can have significant psychosocial impact on patients. No effective treatment besides surgery and radiation is known for craniopharyngiomas, and incomplete knowledge of the molecular mechanisms that drive craniopharyngiomas has hampered the development of targeted therapies for this tumor.

### 1.2 Genetic characterization of craniopharyngiomas

Genetic analysis of 107 craniopharyngiomas revealed activating beta-catenin mutations in 62/65 (95%) of adamantinomatous craniopharyngiomas and BRAF V600E mutation in 39/42 (93%) of papillary craniopharyngiomas and this finding has been validated in subsequent studies (PMID 26927026, 26156055, 25820214, 25442575). The mutations were mutually exclusive and clonal in the two tumor subtypes. To date, our work and that of others has not detected other recurrent mutations or genomic aberrations in either subtype.

### 1.3 Promising activity in case reports of patients with craniopharyngioma

We recently treated a patient who presented with multiply recurrent BRAF V600E craniopharyngioma using dabrafenib (150mg, orally twice daily) and trametinib (2mg, orally twice daily). After 35 days of treatment, tumor volume was reduced by 85%. Mutations that commonly mediate resistance to MAPK pathway inhibition were not detected in a post-treatment sample by whole exome sequencing. A blood-based BRAF V600E assay detected circulating BRAF V600E in the patient's blood. In another recently reported case, a patient with a multiply recurrent papillary craniopharyngioma treated with the BRAF inhibitor vemurafenib also had a dramatic tumor response. Given these promising and unique tumor responses, and the consistent occurrence of the BRAF V600E mutation in nearly all papillary craniopharyngiomas, we propose a Phase II study evaluating the combination of BRAF and MEK inhibition in patients with papillary craniopharyngiomas.

## 1.4 Clinical experience with vemurafenib in other tumors

Vemurafenib (also known as RO5185426, PLX4032, or RG7204) is a low molecular weight, orally available inhibitor of the activated form of the BRAF serine-threonine kinase enzyme, which is commonly found in melanoma. Vemurafenib selectively inhibits oncogenic BRAF kinase. The rationale for identifying such a compound was first provided in 2002, when the high prevalence of activating mutations in the BRAF gene was identified in a variety of cancers, including melanoma. The high level of selectivity of vemurafenib has been demonstrated in biochemical, cell-based, and in vivo assays (see the Vemurafenib Investigator's Brochure for details).

### Summary of clinical efficacy of vemurafenib in melanoma

#### **Phase III, randomized, controlled study (NO25026 [BRIM-3])**

In Study NO25026 (BRIM-3), a global, randomized Phase III study, 675 patients with previously untreated, metastatic melanoma harboring the BRAFV600E mutation were randomly assigned to receive either vemurafenib or dacarbazine between January 2010 and December 2010^12. In the interim analysis for OS and the final analysis for PFS, vemurafenib was associated with a relative reduction of 63% in the risk of death and of 74% in the risk of either death or disease progression, as compared with dacarbazine ( $P < 0.001$  for both comparisons). In the vemurafenib group, most patients had a detectable decrease in tumor size and 106 of 219 patients (48%; 95% CI: 42%–55%) had a confirmed objective response, including 2 patients with a CR and 104 with a PR. Median time to response was 1.45 months. Ten patients in the vemurafenib group were later found to have BRAFV600K mutations; of these, 4 had a PR (40%). In the dacarbazine group, a minority of patients had a detectable decrease in tumor size, and 12 of 220 patients (5%; 95% CI: 3%–9%) met the criteria for a confirmed response (all PRs). The median time to response was 2.7 months. The difference in confirmed RR between the two study groups (48% vs. 5%) was statistically significant ( $P < 0.001$ ).

In a recent post hoc analysis (data cut 1 February 2012), updated survival data censored at crossover showed a median OS of 13.6 months for the vemurafenib treatment arm and 9.7 months for the dacarbazine treatment arm (HR 0.70 [95% CI: 0.57–0.87]  $P < 0.001$ ). The median PFS was 6.9 months with vemurafenib treatment compared to 1.6 months with dacarbazine treatment (HR 0.38 [95% CI: 0.32–0.46]  $P < 0.0010$  (McArthur et al. 2014). This study also assessed efficacy by BRAFV600 mutation type (V600E and V600K). Median OS with vemurafenib in the BRAFV600E group (n=295) was 13.3 months compared with 10.0 months in the dacarbazine group (n=303; HR 0.75 [95% CI: 0.60–0.93]). Median PFS was 6.9 months and 1.6 months respectively (HR 0.39 [95% CI: 0.33–0.47]). For the BRAFV600K mutation group median OS was 14.5 months with vemurafenib (n=33) and 7.6 months with dacarbazine (n=24; HR 0.43 [95% CI: 0.21–0.90]). Median PFS was 5.9 months and 1.7 months, respectively (HR 0.30 [95% CI: 0.16–0.56]).

## 1.5 Combined BRAF and MEK inhibition

Based on nonclinical studies to date, multiple mechanisms of acquired resistance to vemurafenib in BRAFV600-mutated melanoma have been identified which may account for the majority of disease progression:

- Acquisition of activating RAS (NRAS or KRAS) mutations was reported, which accounts for the reactivation of ERK signaling and increased AKT survival signaling
- Spliced isoforms of BRAFV600E were identified which led to enhanced dimerization of BRAFV600E and reactivated the MAPK pathway.
- Increased PDGFRb or IGF1R activity was reported, which may enhance signaling through different RAF isoforms and/or the PI3K/AKT pathway to confer resistance

- Loss of NF1 leads to RAS activation (PMID 24576830, 23288408)

Based on clinical validation data to date, the most prevalent mechanisms of acquired resistance to vemurafenib appear to be the first two mechanisms described above: the acquisition of activating NRAS mutations and spliced isoforms of BRAFV600E, which result in reactivation of ERK signaling in the presence of vemurafenib. The retention of the BRAFV600E mutation in both nonclinical models of vemurafenib resistance and biopsies from patients who progressed on vemurafenib suggests that continued suppression of the pathway by vemurafenib may be required to control tumor cell proliferation; however, reactivation of ERK signaling points to the potential for combination with another agent such as a MEK inhibitor that further inhibits the ERK signaling pathway and, consequently, overcomes the emergence of the pathway-specific resistance in tumors harboring the BRAFV600E. Synergistic anti-proliferative activity was observed when vemurafenib was combined with GDC-0973 in multiple BRAFV600E mutant cancer cell lines. The in vivo combination of vemurafenib with GDC-0973 was also tested in the murine xenograft A375 BRAFV600E mutant melanoma model and in a model of A375 that had acquired resistance to vemurafenib. In both models, the combination of vemurafenib and GDC-0973 is efficacious and well-tolerated and shows greater efficacy than either single agent alone at comparable doses.

### **Phase Ib open-label cobimetinib and vemurafenib study (NO25395; BRIM-7)**

Study NO25395 (BRIM-7) was a Phase Ib study designed to assess the safety, tolerability, and pharmacokinetics of combined MEK inhibition with cobimetinib and BRAF inhibition with vemurafenib. This multicenter study had two stages: a dose-escalation stage and a cohort-expansion stage. This study was being conducted in patients with BRAFV600 mutation-positive, unresectable locally advanced or metastatic melanoma who were either vemurafenib naïve or had progressed on vemurafenib treatment.

All patients in the dose-escalation stage received vemurafenib (720 mg or 960 mg) twice daily in combination with cobimetinib (60 mg, 80 mg, or 100 mg) administered daily according to one of the following 28-day schedules:

- 14 consecutive days of study drug followed by a 14-day drug holiday (14/14)
- 21 consecutive days of study drug followed by a 7-day drug holiday (21/7)
- Continuous daily dose (28/0).

Each treatment cycle was 28 days. There were 10 dose-escalation cohorts of 3–6 patients per cohort. Patients in Cohort 1 received vemurafenib at a dose of 720 mg BID continuously and cobimetinib 60 mg once daily (QD) for 14 consecutive days of each 28-day cycle of combination dosing (14/14). Dose-escalation used the standard 3+3 design and proceeded in increments, taking into account the safety and tolerability of the combination.

Cohorts 1A and 1B were expansion cohorts because both cohorts were declared safe and tolerable after dose escalation; furthermore, they delivered the single-agent maximum tolerated dose and schedule of cobimetinib and, in the case of cohort 1B, the approved dose and schedule of vemurafenib.

### **Randomized phase III study of vemurafenib and cobimetinib (GO28141; CoBRIM)**

This randomized, open-label, multicenter, Phase III study assessed previously untreated patients with metastatic melanoma confirmed by histopathology (unresectable stage IIIC or stage IV) and with a BRAFV600 mutation. In this study, 495 patients were randomly assigned to receive vemurafenib (960 mg BID PO) and cobimetinib (60 mg QD PO) for the first 21 days of each 28 day cycle (combination group) or vemurafenib and placebo (control group). The primary end point was investigator-assessed PFS according to RECIST version 1.1.

### **Clinical efficacy of cobimetinib and vemurafenib in melanoma**

## Study GO28141 (CoBRIM)

Vemurafenib plus cobimetinib was significantly superior to vemurafenib alone: median PFS was 12.3 months in the combination group and 7.2 months in the vemurafenib group (HR 0.58 [95% CI: 0.46-0.72]). The PFS benefit was observed across key subgroups including LDH levels and BRAF mutation type. BORR was 69.9% (95% CI: 63.5-75.3) with 15.8% CRs in the combination arm and 50% (95% CI: 43.6-56.4) with 10.5% CRs in the single-agent arm. OS data are still not mature but interim analysis (data cut-off date of May 2014; ) showed 9-month OS rate of 81% (95% CI: 75-87) for the combination group and 73% (95% CI: 65-80) for the monotherapy group and a HR of 0.65 (95% CI: 0.42-1.00).

## 1.6 Safety

### 1.6.1 Vemurafenib safety summary

AE data from the clinical trials with vemurafenib include events of arthralgia, fatigue, rash, photosensitivity reaction, nausea, alopecia, and pruritus. Vemurafenib also has been associated with reports of well-differentiated cuSCC most of which are the keratoacanthoma (KA) sub-type, or with some features of KA (incompletely expressed or with some features unusual in KA). AEs with vemurafenib have been predominantly mild in severity and transient, even with continuous dosing (over 15 months of treatment in 1 patient). At the recommended Phase II and Phase III dose of 960 mg BID, AEs have been consistent with the safety profile observed in the Phase I setting. Treatment-related Grade 3 AEs and dose-limiting toxicities (DLTs) have been successfully managed by a temporary discontinuation of vemurafenib and/or a reduction in dose. Further details can be found in the current Vemurafenib Investigator's Brochure.

#### Cutaneous squamous cell carcinoma (cuSCC)

In Studies NO25026, NP22657, and NP25163, 79 (23.5%), 34 (25.8%), and 10 (19.2%) patients developed cuSCC/KA. Most cuSCC cases were keratoacanthomas: 58/79 (73.4%) and 30/34 (88.2%) in Studies NO25026 and NP22657, respectively. In the NP25163 study 4/11 (36%) patients had keratoacanthomas.

### **Liver injury**

An analysis of liver-related adverse events reported with vemurafenib use showed that 63 cases (out of an estimated 19,926 patients exposed) of medically confirmed serious adverse events were consistent with drug induced liver injury based on clinical chemistry criteria from the DILI Expert Working Group [126]. Of the 63 cases, two were assessed as severe, both reported as hepatic failure. There were no reported deaths among the 63 cases of liver injury; the outcome of both cases of severe liver injury is considered resolved. The median time to onset of the adverse events was 44 days after initial dose. The median ALT to ALP ratio was calculated as 1.5, suggesting a trend towards cholestatic pattern of liver injury. The analysis did not reveal any risk factors or populations at risk.

### **QT prolongation**

The effects of single and multiple doses of vemurafenib (960 mg bid) on ECG measurement, including the QT interval, were evaluated in 132 adult patients with metastatic melanoma in the Phase 2 study, NP22657.

Vemurafenib treatment at 960 mg bid did not appear to have a clinically meaningful effect on heart rate (HR). The study population-specific correction (QTcP) eliminated most of the bias from the QT-RR relationship and was therefore used for the primary statistical analyses of variables related to the QTc interval.

A total of 41 patients (31.1%) exhibited new ECG changes considered to be abnormal and potentially significant. No patients developed new abnormal U waves, and 19 patients (14.4%) had new abnormal T-waves. Vemurafenib did not cause a meaningful change from the time-matched baseline ECG in either the QRS or the PR (PQ) interval.

Two patients (1.5%) developed treatment-emergent QTcP values >500 msec (CTC Grade 3), while 49 (37.1%) and 6 (4.5%) of patients exhibited treatment-emergent, QTcP values > 450 msec and > 480 msec, respectively. No patients had treatment-emergent uncorrected QT values > 500 msec. Maximal, treatment-emergent, individual QTcP changes >30 msec from baseline were observed in 58 (43.9%) patients, but only one patient (0.8%) exhibited a QTcP change >60 msec from baseline.

The pattern of increasing vemurafenib concentration from Days 1 to 15 of vemurafenib treatment appeared to correlate with the increased mean QTcP change observed from Days 1 to 15 and the constant vemurafenib exposures observed in later cycles appeared to correlate with the maintenance of the effect on QTc interval.

### **Phase I, dose-finding study (PLX 06-02)**

Among patients enrolled in the Phase I study PLX 06-02, the most common vemurafenib-related Grade 2 or 3 toxicities observed were arthralgia, rash, nausea, photosensitivity, fatigue, cutaneous SCC, pruritus, and palmar-plantar dysesthesia. In total, 89% of the toxicities were Grade 1 or 2. Rashes were evenly distributed among face/neck, trunk, and extremities. Four patients had a Grade 4 AE: 2 had elevated gamma-glutamyltransferase (GGT) levels; one had fatigue; and one had reversible pancytopenia of uncertain attribution. Thirteen patients out of 32 total (41%) in the extension cohort required a dose reduction (10 patients to 720 mg BID, one patient to 600 mg BID, and two patients to 480 mg BID).

Phase III, randomized, controlled study (NO25026 [BRIM-3])

An overview of AEs and deaths in Study NO25026 is presented in Table 1. Ninety-nine percent and 91% of patients in the vemurafenib and DTIC treatment groups experienced at least one AE. The majority of AEs were of mild or moderate intensity. The most common AEs (reported in  $\geq 30\%$  of patients) in the vemurafenib group were in the system organ class of skin and subcutaneous tissue disorders, the most common of which were alopecia, rash, and photosensitivity.

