#### Study GO28141 (CoBRIM)

Most patients in both treatment arms experienced at least one AE. The most common AEs, by system organ class, reported in the cobimetinib + vemurafenib arm were: skin and

subcutaneous tissue disorders (83.3%), GI disorders (78%), investigations (68.1%), and general disorders and administrative site conditions (66.9%).

Table 3 tabulates the most common AEs occurring in 20% or more of patients in either study arm by preferred term. The most common AEs that occurred with greater frequency in the cobimetinib plus vemurafenib arm were diarrhea (56.7% vs. 28%), rash (39% vs. 35.6%), nausea (39% vs. 23.8%), blood creatine phosphokinase increased (29.9% vs. 2.9%), photosensitivity reaction (28.3% vs. 15.9%), pyrexia (26% vs. 22.2%), alanine aminotransferase (ALT) increased (23.6% vs. 18%), aspartate aminotransferase (AST) increased (22% vs. 12.6%), and vomiting (21.3% vs. 12.1%).

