### 9.1 Routine adverse event reporting

Adverse event data collection and reporting, which are required as part of every clinical trial are done to ensure the safety of patients enrolled in the studies as well as those who will enroll in future studies using similar agents. Adverse events are reported in a routine manner at scheduled times according to the study calendar in [Section 5.0](#). For this trial, the form "Adverse Events: Solicited" is used for routine AE reporting in Rave.

**Solicited Adverse Events:** The following adverse events are considered "expected" and their presence/absence should be solicited, and severity graded, at baseline and for each cycle of treatment.

CTCAE v4.0 Term	CTCAE v4.0 System Organ Class (SOC)
Blurred vision	Eye Disorders
Diarrhea	Gastrointestinal disorders
Fatigue	General disorders and administration site conditions
Alanine aminotransferase increased	Investigations
Aspartate aminotransferase increased	Investigations
CPK increased	Investigations
Photosensitivity	Skin and subcutaneous tissue disorders
Rash maculo-papular	Skin and subcutaneous tissue disorders

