### 9.2 CTCAE routine reporting requirements

In addition to the solicited adverse events listed in [Section 9.1](#), the following table outlines the combinations of time points, grades and attributions of AEs that require routine reporting to the Alliance Statistics and Data Center. Questions about routine reporting should be directed to the Data Manager.

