**\*Combinations of CTCAE Grade & Attribution Required for Routine AE Data Submission on Case Report Forms (CRFs)**

Attribution	Grade 1	Grade 2	Grade 3	Grade 4	Grade 5
Unrelated			a	a	a

Unlikely			a	a	a
Possible		a	a, b	a, b	a, b
Probable		a	a, b	a, b	a, b
Definite		a	a, b	a, b	a, b

- a) Adverse Events: Other CRF - Applies to AEs occurring between registration and within 30 days of the patient's last treatment date, or as part of the Clinical Follow-Up Phase.
- b) Adverse Events: Late CRF - Applies to AEs occurring greater than 30 days after the patient's last treatment date.

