### 13.4 Supplementary analysis plans

#### 13.4.1 Secondary Endpoints

- **Progression free survival:** progression free survival (PFS) will be estimated using the C Kaplan-Meier method within each cohort. Median PFSs and survival rates will be estimated with their 95% confidence intervals. No formal comparison will be made among the cohorts.
- **Toxicity:** As per NCI CTCAE v 4.0, the term toxicity is defined as adverse events that are classified as possibly, probably, or definitely related to study treatment. Toxicities will be evaluated via the ordinal CTCAE standard toxicity grading. Overall toxicity incidence as well as toxicity profiles by patient and treatment cohort will be explored and summarized. Frequency distributions, graphical techniques and other descriptive measures will form the basis of the analysis. No formal comparison will be made among the cohorts.
- **Response as defined by Enhancing Volume:** Response by Enhancing Volume will be estimated using Response Rate (RR) - where response rate is defined as the number of responses achieved during treatment with BRAF and MEK inhibitors divided by the total number of evaluable patients. For this endpoint, only decreasing volume in enhancing disease will count toward the criteria for response. The same thresholds for CR and PR as seen in Section 11.0 will be used. Point estimates will be generated for response rates within each cohort with corresponding 95% binomial confidence intervals (Duffy and Santner).
- **Response as defined by Non-Enhancing Volume:** Response by Non-Enhancing Volume will be estimated using Response Rate (RR) - where response rate is defined as the number of responses achieved during treatment with BRAF and MEK inhibitors divided by the total number of evaluable patients. For this endpoint, only decreasing volume in non-enhancing disease will count toward the criteria for response. The same thresholds for CR and PR as seen in [Section 11.0](#) will be used.

Point estimates will be generated for response rates within each cohort with corresponding 95% binomial confidence intervals (Duffy and Santner).

- **Overall Survival:** overall survival (OS) will be estimated using the Kaplan-Meier method within each cohort. Median overall survivals and survival rates will be estimated with their 95% confidence intervals. No formal comparison will be made among the cohorts.

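### The toxicity summary sets no minimum grade, yet Grade 1 data are required for some terms and not for others, among them nausea, arthralgia, pyrexia and vomiting

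*Combined protocol and SAP*

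**What the plan says.** **Analysis (Section 13.4.1).** Toxicity, secondary objective 2.2.2, is limited to related events: "the term toxicity is defined as adverse events that are classified as possibly, probably, or definitely related to study treatment". Then: "Toxicities will be evaluated via the ordinal CTCAE standard toxicity grading", and "Overall toxicity incidence as well as toxicity profiles by patient and treatment cohort will be explored and summarized". The section gives no minimum grade and does not say in words that every grade counts.

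**Collection.**
- Section 9.1 lists eight solicited terms: blurred vision, diarrhea, fatigue, ALT, AST, CPK, photosensitivity and maculo-papular rash. For these, "their presence/absence should be solicited, and severity graded, at baseline and for each cycle of treatment".
- Section 9.2 covers other events: "the following table outlines the combinations of time points, grades and attributions of AEs that require routine reporting". In that table the Grade 1 column is empty for every attribution. Grade 2 is required only when the event is possibly, probably or definitely related. Grades 3 to 5 are required for any attribution. The Late CRF, for events more than 30 days after last treatment, starts at Grade 3 and takes related events only.
- Section 9.3.2 requires drug-related special-interest terms at any grade unless a grade is set; nausea and arthralgia are not on the list. Section 9.3.1 does list nausea and vomiting at any grade, but only for Cohort A patients irradiated after the drugs.
- Section 9.4.2, in its list of exemptions from expedited reporting, points Grade 1-3 nausea and vomiting, Grade 1-2 fever and Grade 1-2 arthralgia to routine reporting instead.

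**Background (Section 1.6.1, study PLX 06-02).** "In total, 89% of the toxicities were Grade 1 or 2". The same paragraph names arthralgia and nausea among the commonest Grade 2 or 3 vemurafenib-related toxicities.

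**The concern.** A single incidence table built from these forms would mix two starting points. Diarrhea, fatigue and rash would be counted from Grade 1; nausea, arthralgia, pyrexia and vomiting, if Section 9.2 governs, only from Grade 2. Nothing in Section 13.4.1 would tell the reader. The order of toxicities within the table would then partly reflect the form. The any-grade frequencies in Tables 2 and 3 are the figures a reader will naturally hold beside the result, and for these four terms they would not be like for like.

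The conflict between Sections 9.2 and 9.4.2 adds a second problem. A site that follows 9.4.2 may enter Grade 1 nausea, and a site that follows the 9.2 table need not, so incidence could depend on site as well as on term.

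**Working it through.** **1. Which common terms are affected.** Table 3 prints counts and percentages; the combination-arm denominator, 254, is given in the text on deaths after the table. Count / 254 reproduces every printed percentage above 20%:

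| Term | Count | % of 254 | Solicited in 9.1 |
|---|---|---|---|
| Diarrhea | 144 | 56.7 | yes |
| Rash | 99 | 39.0 | yes, as maculo-papular rash |
| Nausea | 99 | 39.0 | no |
| Arthralgia | 83 | 32.7 | no |
| Fatigue | 82 | 32.3 | yes |
| CPK | 76 | 29.9 | yes |
| Photosensitivity | 72 | 28.3 | yes |
| Pyrexia | 66 | 26.0 | no |
| ALT | 60 | 23.6 | yes |
| AST | 56 | 22.0 | yes |
| Vomiting | 54 | 21.3 | no |

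Seven of the 11 are solicited and four are not. Two pairs show the effect: rash and nausea have the same count (99), and fatigue and arthralgia differ by one (82 and 83), but only the first of each pair is graded from Grade 1. Table 2 (BRAF-inhibitor-naive, n=63) agrees. Its three most frequent terms, diarrhea 52/63 = 82.5%, fatigue 44/63 = 69.8% and photosensitivity 42/63 = 66.7%, are solicited; nausea 36/63 = 57.1% and arthralgia 30/63 = 47.6% are not.

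**2. Whether the 89% sizes the loss.** It cannot be reproduced: no numerator, denominator or split between Grades 1 and 2 is given. It counts toxicities, not patients, and comes from vemurafenib alone. Related Grade 2 events are collected, so only the unknown Grade 1 part matters.

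**3. What the loss could be, by assumption only.** Let p be the any-grade incidence and g the share of affected patients whose worst grade is 1. If the 9.2 table governs, recorded incidence = p × (1 − g). The documents do not give g. I let it run from 0 to 0.89, the upper end being the extreme in which the whole Grade 1 or 2 share is Grade 1. Counts are 16 × p × (1 − g), for one cohort of 16:

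| g | Nausea (p = 39.0%) | Arthralgia (p = 32.7%) |
|---|---|---|
| 0 | 39.0% (6.2) | 32.7% (5.2) |
| 0.25 | 29.2% (4.7) | 24.5% (3.9) |
| 0.50 | 19.5% (3.1) | 16.3% (2.6) |
| 0.75 | 9.7% (1.6) | 8.2% (1.3) |
| 0.89 | 4.3% (0.7) | 3.6% (0.6) |

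The range runs from no loss to nearly total loss, so it is not an estimate. The inputs are also imperfect: Table 3 concerns melanoma and is not restricted to related events, whereas Section 13.4.1 is. If 9.4.2 governs and sites follow it, the loss for these terms disappears.

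**4. Which floor is common to all terms.** Under 9.2, related Grade 2 is required for every term from registration to 30 days after last treatment. Under 9.4.2, the four terms are reported from Grade 1, which includes Grade 2. Related events at Grade 2 or higher in that window are therefore required under either reading. After the window the assured floor is Grade 3: the Late CRF starts there, and the footnote that extends the Other CRF to clinical follow-up leaves late Grade 2 capture unclear.

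**The case against.** The strongest reply is Section 9.4.2. It directs Grade 1 nausea, vomiting, fever and arthralgia to routine reporting, so it cannot be said flatly that these data are not collected. This stands as a limit on the claim, but it does not remove the problem. The text sits in a list of exemptions from expedited reporting, and the routine rule it points to is Sections 9.1 and 9.2, where these terms are not solicited and Grade 1 is blank. Either 9.2 governs and the starting grades differ, or the two sections conflict.

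It can also be said that soliciting expected terms at all grades and the rest from Grade 2 is a visible design choice, that the endpoint is descriptive with no formal comparison, and that a footnote on collection thresholds would be enough. The first two are true and keep the point small. A footnote would disclose the mixture but would not make the incidences comparable.

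A reader might infer from Section 1.6.1 that most nausea and arthralgia would be lost. The documents do not support that: the 89% pools Grades 1 and 2, and the sentence placing arthralgia and nausea among the commonest toxicities concerns Grades 2 and 3, which the form collects when related.

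**Conclusion.** The point holds in a limited form. Section 13.4.1 sets no grade floor while the collection floor differs by term, and Sections 9.2 and 9.4.2 disagree on Grade 1 for four common toxicities. Several common toxicities are affected, not all of them. A reader might conclude that the profile understates the regimen's commonest toxicities in general; that does not follow, because seven of the 11 terms above 20%, including the most frequent, are solicited at every grade. Nor does Section 13.4.1 state that incidence covers all grades; that is an inference from its silence.

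The size of any understatement cannot be derived from the documents. The conclusion rests on the 9.2 table being followed as printed and on Table 3 being a fair guide to which terms will be common here. Nothing changes for the primary endpoint (response) or for the adverse event stopping rule in Section 13.5.1, which counts Grade 4 or higher. This is a minor improvement, worth making because it is cheap.

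**What to change.** - In Section 13.4.1, report overall incidence and the term-by-term profile of related events at Grade 2 or higher, from registration to 30 days after last treatment.
- Show Grade 1 in a separate table limited to the solicited terms and the special-interest events collected at any grade.
- Report events more than 30 days after last treatment separately, at Grade 3 or higher.
- Reconcile Section 9.2 with Section 9.4.2, so that sites have one rule on Grade 1 nausea, vomiting, fever and arthralgia.
- Optionally, for any patients still to be treated, add nausea and arthralgia to the solicited list in Section 9.1.

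The cost is a few sentences in Section 13.4.1, two extra tables, one clarification in Section 9 and, if the option is taken, two lines on the solicited form. The main changes need no new data. The downside is that Grade 1 data on solicited terms move out of the main profile, so its headline becomes a Grade 2 or higher figure and can be set against the any-grade rates in Tables 2 and 3 only for terms shown in the Grade 1 table.
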